### Study design

A randomized, double-blind, placebo-controlled, crossover study design with a 2-week washout period was used. After study enrollment, participants were randomly assigned to either the BE supplement group or the placebo control group. All data collections were performed at the same time of day ( $\pm 1\text{h}$ ) after an overnight fast, and participants were asked to abstain from caffeine, alcohol, high intake of antioxidant-rich foods or supplements, and excessive exercise for at least 48 hours prior to their visits. Participants were also informed to not change their dietary habits during the study period. Descriptive measurements of height, weight, BMI, body composition, and hand grip strength were taken at both BE and placebo visits. Baseline measurements of RHR, BP, blood sampling for TAC, endothelial function, skeletal muscle oxygen utility capacity during exercise, and muscular fatigue index were assessed. Participants then consumed either the BE or placebo, and all baseline measures were repeated as experimental measures 1 hour after BE or placebo intake. A 1-hour digestion period was chosen because anthocyanins have been shown to reach peak levels in the blood within 1-hour post consumption. After 2 weeks each participant returned for a second visit and the same protocol was repeated with the intervention (BE or placebo) they did not receive in the first visit. All women (n = 9) were tested during the early-to-mid follicular (days 1 – 10) and late-luteal phases (> day 19) of the menstrual cycle in order to avoid confounding effects of endogenous estrogen on autonomic function.

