#### Resting heart rate and blood pressure

RHR and BP were assessed before and after BE and placebo intake. Participants rested in a seated position in a quiet room for 5 minutes and were informed not to talk or move during this time. RHR, systolic BP, and diastolic BP were measured using an automated sphygmomanometer (Omron Blood Pressure Monitor BP786N, Omron Healthcare, Inc., Lake Forest, IL) in duplicate. The two measurements of the RHR and BP were averaged and recorded as the resting values.

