#### Blood sampling

Blood samples were collected from an antecubital vein by a trained phlebotomist using EDTA tubes before and after BE and placebo intake. Samples were centrifuged at 3500 rpm for 10 minutes at 4°C. Plasma samples were stored at -30°C for later analysis of total antioxidant capacity (TAC). TAC was assessed using a commercially available Total Antioxidant Capacity Assay Kit (CAT#: ab65329, Abcam, Cambridge, UK) according to the manufacturer's instructions. After incubating samples at room temperature (23°C), absorbances were measured at 570nm using a microplate reader. The average intra-assay and inter-assay coefficient of variation for TAC were 6.3% and 2.9%, respectively.

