#### Statistical analysis

A Shapiro-Wilk's test was used to determine normal distribution of the data. Independent t-tests were used for evaluating baseline characteristics at the BE and placebo visits. Dependent variables were assessed using a  $2 \times 2$  repeated measures analysis of variance (ANOVA) [group (BE and placebo)  $\times$  time (before and after supplement intake)] to determine differences between pre- and post-BE and placebo intake. If a significant effect was noted, paired t-tests were used for post hoc comparisons. All statistical analyses were performed with SPSS 26.0 (IBM, Armonk, NY). Data are presented as Mean  $\pm$  SD unless noted otherwise. Statistical significance was set to  $p < 0.05$ . It was calculated that a minimum of 16 total participants in a crossover design (16 each group, BE and placebo) would enable 80% power to observe a 3 to 5% change in FMD between the two groups. An effect size analysis was performed using Cohen's d and interpreted 0.2, 0.5, and 0.8 as small, medium, and large effect sizes, respectively.

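### About nine outcomes are each tested at p < 0.05 with no primary outcome or deciding contrast named, so a null FMD result can be displaced by another outcome or by a within-condition comparison

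*Combined protocol and SAP*

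**What the plan says.** All references are to the combined protocol and SAP.

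- **Outcomes.** Study design lists the domains: "Baseline measurements of RHR, BP, blood sampling for TAC, endothelial function, skeletal muscle oxygen utility capacity during exercise, and muscular fatigue index were assessed". All are repeated one hour after intake. The measurement sections break them down further. For the first two domains, "RHR, systolic BP, and diastolic BP were measured" in duplicate and averaged. The NIRS section names three recorded signals (StO2, [O2Hb], [HHb]) but defines no summary value for any of them.
- **Test.** In Statistical analysis, "Dependent variables were assessed using a" 2 × 2 repeated measures ANOVA, group (BE, placebo) by time (before, after). The dependent variables are not listed there.
- **Threshold.** "Statistical significance was set to" p < 0.05, once, for everything. No adjustment is mentioned.
- **Follow-up.** "If a significant effect was noted, paired t-tests were used for post hoc comparisons". Which effect (group, time or interaction) opens this step is not said.
- **Sample size.** A minimum of 16 crossover participants "would enable 80% power to observe a 3 to 5% change in FMD between the two groups". This is the only place where FMD is set apart, and it is not called primary.

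**The concern.** The plan fixes a threshold for each test but not what would count as evidence that the supplement works. Two gaps combine.

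First, no outcome ranks above another. If FMD is null, any of the other outcomes can be brought forward at the full 5% level without departing from the written plan.

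Second, no ANOVA effect is singled out. Only the group × time interaction compares the pre-to-post change on BE with that on placebo. As written, a time effect shared by both conditions also opens the paired t-tests. Those tests can then be significant in one condition and not in the other by chance. Reading that pattern as a supplement effect gives up the placebo comparison for which the crossover was run. Exercise and cuff occlusion are repeated within a visit, so a shared pre-to-post shift is possible, although the documents give no size for one.

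**Working it through.** **The plan's own figure.** The 16 participants for 80% power cannot be reproduced, because no SD is given. Solving backwards for a two-sided paired t-test at 0.05 with n = 16, 80% power needs a standardised difference of 0.749. The implied SD of paired differences is 3/0.749 = 4.0 for a 3% change and 5/0.749 = 6.7 for a 5% change. This does not affect the present point, but it confirms that only FMD was considered in sizing the trial.

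**Inputs.**
- Outcomes: RHR, systolic BP, diastolic BP, TAC, FMD, StO2, [O2Hb], [HHb] and fatigue index, which makes nine. The count is inferred, with one summary per NIRS signal. Hand grip and body measures are labelled descriptive and left out.
- Threshold: 0.05 per test (Statistical analysis). Sidedness is not stated; two-sided is assumed, as F-tests are non-directional.
- Participants: 18 (Participants section).
- Correlation among outcomes: not given. It is assumed common to all pairs and varied from 0 to 0.9.

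**Reading A: any significant interaction counts.** For each outcome the interaction test is a one-sample t-test on (BE after − BE before) − (placebo after − placebo before). With independent outcomes and no true effect:

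1 − (1 − 0.05)^9 = 1 − 0.630 = 0.370.

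With correlated normal outcomes (20,000 simulated null trials, n = 18):

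| Common correlation | At least one false interaction |
|---|---|
| 0 | 37% |
| 0.3 | 33% |
| 0.5 | 27–28% |
| 0.7 | 21% |
| 0.9 | 13% |

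If correlation of 0.5 to 0.9 exists only within the heart rate/BP set and within the NIRS set, the rate is 35.5% to 28.3%. Counting only the six listed domains, independently, gives 1 − 0.95^6 = 26%.

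**Reading B: a significant interaction plus a significant post hoc test.** With no time effect and correlation 0.7 to 0, the rate is about 8% to 14% if the BE before–after test must also be significant. It is about 12% to 22% if either that test or the after-intake BE–placebo test suffices.

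**Reading C: any ANOVA effect opens the gate, and *BE changed, placebo did not* is taken as a supplement effect.** With no time effect, the rate is about 14% to 24% (correlation 0.7 to 0). With an assumed time shift of 0.5 within-visit SD, identical in both conditions, it is 50% (correlation 0.7) to 82% (correlation 0). The 82% corresponds to about 17% per outcome, since 1 − (1 − 0.174)^9 = 0.82. Under this reading, a single outcome already exceeds 5% before multiplicity is considered.

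**The case against.** **There is no either/or success rule.** The plan gives a per-test threshold and never says that one positive outcome establishes efficacy. Family-wise error describes a claim of that kind, and the documents do not make it. This stands: the rates above are conditional on how results are read. But the plan does not exclude any of those readings.

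**FMD is the natural implied primary.** It alone drives the sample size. This is reasonable, and on that view its interaction test keeps its 5% level. A reader might infer that the other eight tests prevent a clean answer on FMD. They do not, because testing other outcomes leaves the FMD interaction test unchanged. What is missing is a statement that FMD ranks first and that the rest cannot take its place.

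**The group main effect.** A reader might count it as a second route to a positive result, giving 18 tests and 1 − 0.95^18 = 60% (38% at correlation 0.7). The documents do not support that. The main effect averages values before and after intake, so half of it precedes dosing, and nothing says it would be read as efficacy.

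**The count and the correlations are assumptions.** This is true and limits precision. At the extreme of 0.9 across all nine outcomes, Reading A still gives 13%.

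**Adjustment is a matter of preference in a small acute study.** This is fair. Naming one deciding test and labelling the rest exploratory meets the concern without it.

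**Timing.** The text is in the past tense and reports enrolment and assay variation. A primary outcome named now may be retrospective. The documents mention registration but do not reproduce what was registered. This objection shapes the fix.

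**Conclusion.** The point holds and should be addressed; it does not invalidate the trial. The plan leaves the deciding outcome and the deciding contrast open, so the stated 5% does not bound the error of a claim that the supplement affects at least one outcome. With no true supplement effect, that error is 13% to 37% if any interaction counts (correlation 0.9 to 0). It is about 8% to 22% if a post hoc test must also be significant (no time effect, correlation 0.7 to 0). It is 50% to 82% if a shared time effect opens the gate and within-condition tests are compared (0.5 SD shift, correlation 0.7 to 0).

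These figures rest on an inferred count of nine outcomes, normal data, n = 18, and correlations and a time shift that the documents do not supply. The practical risk is selective emphasis, not an inflated FMD interaction test.

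**What to change.** Amend Statistical analysis to say:

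- The only test of a supplement effect is the group × time interaction, that is, the BE-minus-placebo difference in pre-to-post change. Paired t-tests follow only a significant interaction and do not by themselves support a claim of effect.
- FMD, the outcome on which the trial was sized, is primary at two-sided 0.05. State whether this was set before the data were seen and, if so, where and when it was recorded. If not, say that it was designated afterwards.
- The other outcomes are listed by name, with one defined summary per NIRS signal, and are exploratory. Each is reported as a BE–placebo estimate with a 95% confidence interval. None supports a stand-alone efficacy claim or replaces a null FMD result.

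**Cost.** A few sentences and no new data. FMD keeps its full 5% level and its power. The price is that no stand-alone significance claim can be made for the other outcomes. Holm adjustment over those eight is an option if formal claims are wanted. An effect with 80% power at 0.05 (standardised difference 0.70, n = 18) would have about 47% at the first Holm step, 0.05/8 = 0.00625.
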